## 9.2 Sample Size and Randomization

We will aim for 2500 enrolled participants to result in a 99% power for statistical significance, assuming no difference in AAD, OAC, or CA use rates between those with ICM and non-ICM monitoring methods. We cannot control the exact number of subjects but will attempt a 1:1 allocation into the ICM and non-ICM arms to result in 1250 patients each.

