### **4.2 Inclusion Criteria**

- Patients > 18 years of age
- Present for management of AF
- ICM is inserted at the discretion of the treating physician

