## 6 STUDY PROCEDURES

### 6.1 Description of Evaluation

*Table 1. Variables for data collection will include but are not limited to the following.*

Variables	Description and Definition
Age	## Years
Gender	0 = Male, 1 = Female
BMI	## kg/m2
Race	0 = Caucasian, 1 = African American, 2 = Hispanic, 3 = Asian, 4 = Other
Hypertension	0 = No, 1 = Yes
Hyperlipidemia	0 = No, 1 = Yes
Diabetes Mellitus	0 = No, 1 = Yes
Coronary Artery Disease	0 = No, 1 = Yes
CVA/TIA	0 = No, 1 = Yes
Peripheral Artery Disease	0 = No, 1 = Yes
Obstructive Sleep Apnea	0 = No, 1 = Yes
Compensated HF (EF > 35%)	0 = No, 1 = Yes
History of Smoking	0 = No, 1 = Yes
Thyroid Dysfunction	0 = None, 1 = Hypothyroidism, 2 = Hyperthyroidism
Chronic Obstructive Pulmonary Disease	0 = No, 1 = Yes
Gastrointestinal Disorders	0 = No, 1 = Yes
CHADS 2 /VASC 2 Score	##
Antiarrhythmic Drug	
History of Cardioversion	0 = No, 1 = Yes
Baseline AAD Use	0 = No, 1 = Yes
Duration of Arrhythmia	## Mos.
Left Atrial Size	## cm.
Left Ventricular Ejection Fraction	## %
Access to EP	0 = No, 1 = Yes
Compliance to OAC	0 = No, 1 = Yes
Attempted AAD	0 = No, 1 = Yes
Need for Catheter Ablation	0 = No, 1 = Yes
Time to Catheter Ablation	## Days
Number of Monitors used Post-CA	##

Type of Monitors Used	0 = MCOT, 1 = 48-Hr Holter
Need for Redo Ablation	0 = No, 1 = Yes
Time to Redo Ablation	## Days
CV-Related Hospital Duration	## Days
Length of Stay	## Days
AF-Related Hospitalization	0 = No, 1 = Yes
HF-Related Hospitalization	0 = No, 1 = Yes
Bleeding Complication	0 = No, 1 = Yes
Stroke and TIA	0 = No, 1 = Yes
Freedom of AF at 12 Mos.	0 = No, 1 = Yes
Continued OAC Use	0 = No, 1 = Yes
Continued AAD Use	0 = No, 1 = Yes

Abbreviations: BMI – body mass index, CVA = cerebrovascular accident, TIA – transient ischemic attack, AAD = antiarrhythmic drug, CV – cardiovascular, CA = catheter ablation, AF – atrial fibrillation, HF – heart failure, OAC – oral anticoagulation, MCOT – mobile cardiac outpatient telemetry

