## 9.3 Outcomes

Primary	Secondary

• Access to care

• Time of AAD initiation

• Time of OAC initiation

• Time to CA

• Any changes or discontinuation of AAD post-ablation

• Any changes or discontinuation of OAC post-ablation

• Arrhythmia recurrence

• Redo Ablation

	

• Systemic thromboembolic events

• All AF and cardiovascular related hospitalization

• Heart failure exacerbations

• Bleeding complications

• Cardiovascular mortality

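### The 99% power in Section 9.2 is stated on all 2500 enrolled patients, makes no allowance for the smaller ablated subset, and is unsupported for the post-ablation primary outcomes

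*Combined protocol and SAP*

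**What the plan says.** Section 9.2 (Sample Size and Randomization) states: "We will aim for 2500 enrolled participants to result in a 99% power for statistical significance". It continues "assuming no difference in AAD, OAC, or CA use rates between those with ICM and non-ICM monitoring methods" and says the study "will attempt a 1:1 allocation into the ICM and non-ICM arms to result in 1250 patients each". It names no outcome, effect size, event rate or expected ablation rate.

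Section 9.1 points forward to the endpoint list in 9.3, which has eight primary outcomes. Two are restricted to the period after an ablation: "Any changes or discontinuation of AAD post-ablation" and "Any changes or discontinuation of OAC post-ablation". A third is redo ablation, which presupposes a first one.

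Ablation is not required for entry. The relevant inclusion criterion in 4.2 is "Present for management of AF". Section 5.1 leaves CA to the physician's preference, and Table 1 in 6.1 records "Need for Catheter Ablation" as No or Yes. Section 4.3 excludes patients ablated before ICM implant, so patients in the ICM arm can be ablated only after the implant. Chart review runs for 12 months after enrolment.

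**The concern.** A power figure belongs to a comparison with a stated number of analysed patients. Here the number is everyone enrolled, while two primary outcomes exist only for ablated patients, and for a third only ablated patients can have the event. For the two drug outcomes the denominator shrinks again, because a patient must be taking the drug at ablation for it to be changed or stopped.

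What is at stake is how a non-significant result is read. Against a stated power of 99%, a null finding on post-ablation AAD use, OAC use or redo ablation would look like strong evidence that ICM makes no difference. If the analysed number is much smaller than 1250 per arm, that inference is not available. These outcomes bear directly on whether ICM changes management after ablation.

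**Working it through.** **Inputs from the documents.** 2500 enrolled, 1250 per arm, power 99% (9.2); significance level 0.05 (9.4). Two-sided testing is stated in 9.4 for the t-tests and is assumed here for the rest.

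**Inputs not in the documents.** The share f of each arm that is ablated (assumed equal in both arms, in line with 9.2's assumption of no difference in CA use), and the effect size.

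**Step 1: the plan's own figure.** The 99% cannot be reproduced, because no effect, rate, standard deviation or hazard ratio is given. Taken literally, no difference between arms gives a rejection probability of 5%. Solving backwards, 99% at 1250 per arm corresponds to, for example, 10.0% v 15.7%, 30.0% v 38.1% or 50.0% v 58.5%, or a standardised mean difference of 0.171. None of these is in the documents.

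**Step 2: the same effect in the ablated subset.** For 99% power at two-sided 0.05, the noncentrality with 1250 per arm is 1.960 + 2.326 = 4.286. It scales with the square root of the analysed number, so

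power(f) = Φ(4.286 × √f − 1.960).

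| Assumed f | Ablated per arm (1250 × f) | 4.286√f − 1.960 | Power |
|---|---|---|---|
| 100% | 1250 | 2.326 | 99.0% |
| 80% | 1000 | 1.874 | 97.0% |
| 60% | 750 | 1.360 | 91.3% |
| 50% | 625 | 1.071 | 85.8% |
| 40% | 500 | 0.751 | 77.4% |
| 30% | 375 | 0.388 | 65.1% |
| 20% | 250 | −0.043 | 48.3% |

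A direct two-proportion calculation, using the back-solved differences from 10%, 30% and 50%, agrees to within 0.2 points (for example 85.7% at f = 50% and 48.1% at f = 20%). Power falls below 90% when f is under about 57%, and below 80% when f is under about 43%.

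**Step 3: drug outcomes.** Replace f by f × d, where d is the share of ablated patients on the drug at ablation. As an illustration with both values assumed, f = 60% and d = 50% give 0.60 × 0.50 = 30%, hence 65.1%.

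**Step 4: detectable difference.** With an assumed base rate of 50%, the difference detectable with 99% power is approximately 4.286 × √(2 × 0.25 / n):

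- n = 1250 per arm: 8.6 points
- n = 625 per arm: 12.1 points
- n = 375 per arm: 15.7 points

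**Step 5: how far the result depends on the effect.** The loss in Step 2 holds for an effect that gives exactly 99% in the full sample. A larger effect loses less: 30% v 45% still has 99.9% power at f = 40%.

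**The case against.** A reader might infer that the 99% is shown to be false for three of the eight primary outcomes. The documents do not support that. They give no effect size and no ablation share. At f of 80% or more the loss is about 2 points or less, and a larger effect in the ablated subset could keep power at 99%. Near-even odds of detection arise only at f of about 20%. What stands is that the figure is unsupported for these outcomes and is lower at the same effect.

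A reader might also infer that all three outcomes can be analysed only in ablated patients. That is strict for the two drug outcomes. Redo ablation is a No/Yes item in Table 1 with no stated restriction and could be tabulated over everyone, with non-ablated patients scored No. That version mixes uptake of a first ablation with the risk of a second, so it answers a different question, but it is possible. If redo ablation is analysed by Cox regression, power depends on events rather than patients. The events still come only from ablated patients, so at a fixed redo risk and hazard ratio their number falls in proportion to f.

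Next, 9.2 does not tie the 99% to these outcomes. Sections 3 and 5.1 describe a primary outcome of AF freedom with continued AAD and OAC use, which applies to every patient, and the 99% may have been meant for that. This is fair, and it is why the fix starts by naming the outcome. It does not remove the point, because 9.1 refers the reader to the 9.3 list, where the post-ablation items are primary and no other power is given for them.

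Finally, the deeper defect is that the 99% has no stated effect behind it for any outcome. That is true. But supplying an effect size and recalculating on 1250 per arm would still leave the wrong denominator for the post-ablation outcomes, so the point is not absorbed by that one.

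**Conclusion.** The point holds in this form: 9.2 states one power figure on all enrolled patients and makes no allowance for primary outcomes that concern only ablated patients. For AAD and OAC change after ablation, and for redo ablation analysed among those at risk of it, the 99% is unsupported and, at the effect that gives 99% in the full sample, necessarily lower.

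The size is conditional. It rests on an ablated share that the documents do not give, on equal shares in both arms, on two-sided 0.05, and on carrying the full-sample effect into the subset. Over assumed shares from 80% down to 20%, power runs from about 97% to about 48%, with a further reduction for the drug outcomes. Nothing in the plan shows where in that range the study will fall.

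**What to change.** In 9.2:

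- Name the outcome to which the 99% applies, with the rates or effect size assumed in each arm. Do not simply keep the figure for the remaining outcomes, since it cannot at present be reproduced for any of them.
- Say that it does not apply to AAD change, OAC change or redo ablation after a first ablation. For these, state power or detectable difference on the expected number ablated per arm, 1250 × f, and for the drug outcomes on 1250 × f × d. The sites can count f and d from the records they already query for screening (4.1.1).
- Say whether redo ablation is analysed among ablated patients or over all enrolled.

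If the restated power is low, report these outcomes with confidence intervals and state that a non-significant result will not be read as evidence of no difference. Section 9.4 plans confidence intervals with its Cox models, but not for the chi-square comparisons that would serve the drug outcomes.

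The cost is a few lines of text and a count from existing records. No added enrolment is needed. The downside is a less favourable stated power for these outcomes.

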## **3 STUDY DESIGN**

We propose a multi-center, retrospective study to evaluate the use of ICM versus traditional, non-ICM methods such as ECGs, Holter, and mobile cardiac outpatient telemetry (MCOT) units, referred to as non-ICM from here on out, from 2018 to 2021. The primary outcome will be the evaluation of AF freedom at 12 months with continued AAD and OAC use. Secondary outcomes are described above. This study will be approved by the Institutional Review Board (IRB), and patient consent will not be required due to the nature of the study.

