## **5 STUDY INTERVENTIONS**

### **5.1 Interventions, Administration, and Duration**

No intervention or administration will be performed due to the observational nature of each phase. Charts of patients enrolled in the study will be reviewed for an initial monitoring method, any changes in

management, including AAD, OAC, CA, as per physicians' preference, arrhythmia recurrence, need for redo CA, and AF-related complication, for 12 months after enrollment. Lastly, the primary outcomes of AF freedom and continued AAD and OAC use will be noted at the end of the study duration.

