## 9 STATISTICAL CONSIDERATIONS

### 9.1 General Design Issues

The null hypothesis is that there is no difference in outcomes between patients who underwent ICM insertion versus more traditional monitoring methods. Patients who start with traditional monitoring can cross into the ICM group at any time throughout the study. Primary and secondary endpoints are described below.

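### The 99% power in Section 9.2 is tied to no stated outcome, base rate or difference, and the primary outcome in Sections 1.1, 3 and 5.1 does not match the eight primaries in Section 9.3

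*Combined protocol and SAP*

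**What the plan says.** **Power.** Section 9.2 aims for 2500 patients, 1250 per arm, and claims "99% power for statistical significance, assuming no difference in AAD, OAC, or CA use rates between those with ICM and non-ICM monitoring methods". It concedes that the arm sizes cannot be controlled. Section 9.1 states a null of no difference in outcomes, without saying which, and adds: "Patients who start with traditional monitoring can cross into the ICM group at any time throughout the study".

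**Primary outcome.** Section 3: "The primary outcome will be the evaluation of AF freedom at 12 months with continued AAD and OAC use". The second bullet of Section 1.1 and the end of Section 5.1 also name AF freedom and continued AAD and OAC use; Section 5.1 treats them as several primary outcomes. Section 9.1 then says "Primary and secondary endpoints are described below", and Section 9.3 lists eight primaries: access to care, timing of AAD start, timing of OAC start, time to CA, post-ablation AAD changes, post-ablation OAC changes, arrhythmia recurrence and redo ablation.

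**Secondary outcomes.** Section 3 says "Secondary outcomes are described above". The only such text above it is Section 1.2, which covers differences in CA and AAD and AF-related complications.

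**Threshold.** Section 9.4 sets p < 0.05, with no hierarchy or adjustment.

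**The concern.** A power figure means something only for a named outcome, a base rate and a difference. Section 9.2 gives none of these, and its one condition is an absence of difference. A reader cannot tell what 1250 per arm can detect, yet 99% invites the view that a null result would be decisive.

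The primary outcome is also defined in two ways that are not equivalent, and the documents do not say which governs. The study is retrospective, so the outcomes already sit in charts. While both definitions stand, which result is called primary can be decided once the results are known.

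**Working it through.** **1. Can the 99% be reproduced?** Inputs in the documents: 1250 per arm (9.2), 0.05 (9.4), two-tailed (9.4, stated for t-tests). No base rate, difference, hazard ratio, event count or standard deviation appears anywhere. The possible readings are:

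- *The use rates are tested.* With a true difference of zero, the chance of p < 0.05 is alpha, 5%, at any base rate.
- *Co-treatment is assumed balanced, or the null is restated loosely.* No alternative is given, so no power follows.
- *Non-inferiority at zero difference.* From a 50% base, 99% power would need a margin of (1.960 + 2.326) × √(2 × 0.25/1250) = 8.6 points. No margin is stated, and Section 2.2 hypothesises superiority.

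None of these yields the 99% from stated inputs.

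**2. What 1250 per arm can detect.** Base rates are my assumption. For two proportions, power = Φ[(|d| − z·s0)/s1], where s0 = √(2p̄(1−p̄)/n) and s1 = √([p1(1−p1) + p2(1−p2)]/n).

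For 50% v 58.5%: p̄ = 0.5425, s0 = 0.01993, s1 = 0.01985. (0.085 − 1.960 × 0.01993)/0.01985 = 2.31, so power is 99%.

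| Assumed base | 99% power | 80% power |
|---|---|---|
| 50% | ±8.5 points | ±5.6 points |
| 30% | +8.1 / −7.5 | +5.3 / −5.0 |

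Power for 5 points from 50% is 71%. With 500 v 2000 patients, 99% power from 50% needs 10.6 points.

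Crossover, if 10% or 20% of the non-ICM arm cross and gain the full ICM effect (assumption): power for 8.5 points is 97% or 93% if they stay counted as non-ICM, and 98.9% or 98.7% if they are moved to ICM. Other biases from moving them are not counted.

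**3. The primary definitions side by side.**

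| Sections 1.1, 3, 5.1 | Nearest item in 9.3 | Gap |
|---|---|---|
| AF freedom (12 months in Section 3) | "Arrhythmia recurrence" | No time point; Section 5.1 lists recurrence separately ("arrhythmia recurrence, need for redo CA, and AF-related complication, for 12 months after enrollment") from AF freedom |
| Continued AAD and OAC use | "Any changes or discontinuation of AAD post-ablation", and the same for OAC | Ablated patients only |
| None | Access to care; AAD, OAC and CA timing; redo ablation | Primary only in 9.3 |

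Section 1.2 places CA and AAD differences among the secondaries, whereas 9.3 makes time to CA and timing of AAD start primary. This last conflict depends on reading differences in use as including timing.

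**4. Multiplicity, if any one of the eight counts as success.** Under independence, 1 − 0.95^8 = 0.337. The upper bound is 8 × 0.05 = 0.40. With equal correlation of 0.5 or 0.8 (assumption) it is 25% or 16%.

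**5. Power if all eight stay primary.** The strictest Holm step is 0.05/8 = 0.00625 (z = 2.734).

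- *Binary outcome in all 1250 per arm, 50% v 58.5%:* (0.085 − 2.734 × 0.01993)/0.01985 = 1.54, so power is 94%; 99% needs about 10 points.
- *Ablated-only outcomes (post-ablation AAD changes, post-ablation OAC changes, redo ablation):* if 30% to 50% of each arm is ablated (assumption), n is 375 to 625 per arm. Power for 8.5 points is 34% to 61%, and 99% needs 18.0 to 14.1 points.
- *Timing outcomes (AAD start, OAC start, CA):* these need a hazard ratio and an event count, which the documents do not give.

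**The case against.** - **The clause may only be loose drafting.** It may restate the null or assume balanced co-treatment, and 9.3 lists no simple use rates, so the 5% reading is the least plausible. That stands: the 99% cannot be checked, but it is not shown to be a miscalculation.
- **The intended primary can be inferred.** Table 1 already has yes/no fields for AF freedom at 12 months and for continued OAC and AAD use, matching Sections 1.1, 3 and 5.1, and parts of 9.3 overlap with them. This is good evidence of intent, but 9.1 sends the reader to 9.3, so the conflict remains.
- **AF freedom has its own weakness as a primary.** Continuous monitoring can find more AF. If true recurrence were 50% in both arms, and ICM missed none while other monitoring missed 17% (assumptions), recorded AF freedom would be 0.50 × 0.17 = 8.5 points lower with ICM. This stands as a caveat. The threefold detection increase in Section 2.1 concerns cryptogenic stroke, syncope and post-ablation settings, and Section 4.3 excludes ICMs inserted for stroke or syncope and CA before ICM implant, so it does not size the effect here.
- **Multiplicity depends on a success rule that no section states.** That stands: 34% to 40% is conditional and does not carry the point.

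A reader might also infer that 2500 is too few. The documents do not support that: with no target difference stated, no shortfall can be shown.

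**Conclusion.** The concern holds in two parts. First, the 99% is an unsupported power statement; this needs no assumption, because the inputs are absent. Second, the primary outcome is unreconciled between Sections 1.1, 3 and 5.1 and Section 9.3, at one unadjusted 0.05. The second is the more serious, because it leaves open which result counts.

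A reader might conclude that the 99% is arithmetically false, or that the primary will in fact be picked from the results. The documents show neither: the figure cannot be checked, and the text permits such a choice without indicating that one is planned.

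All detectable differences rest on assumed base rates, ablated shares and crossover, and on the normal approximation for two proportions.

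**What to change.** 1. **One primary, before analysis.** Reconcile Sections 1.1, 1.2, 3 (including its backward pointer), 5.1, 9.1 and 9.3. AF freedom at 12 months is the natural candidate because Sections 1.1, 3 and 5.1 name AF freedom and Table 1 already collects it at 12 months; the choice is the sponsor's. State whether continued AAD and OAC use is part of it or a separate secondary, and that continuous monitoring may lower recorded AF freedom in the ICM arm without a true difference.
2. **Section 9.2.** Delete the no-difference clause. Suggested wording, with the sponsor's own base rate and reason for the difference: *For AF freedom at 12 months, 1250 per arm at two-sided 0.05 gives 99% power for about 8.5 percentage points, and 80% power for about 5.6, from an assumed 50%.* Add the values for unequal arms and state the arm in which crossovers are counted.
3. **If the 9.3 list stays primary.** Apply Holm across the eight and state power for each outcome, using the ablated number for post-ablation items and a hazard ratio and event count for timing items. Add to Table 1 any variables it lacks: timing of AAD and OAC start, arrhythmia recurrence and post-ablation AAD and OAC changes. The table is not exhaustive, so some may already be planned.
4. **Remaining outcomes.** Report them as secondary, as estimates with confidence intervals.

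Cost: text changes and no change in enrolment. The stated power becomes conditional on an assumed base rate and difference, and fewer outcomes can be called primary. Keeping all eight may need a few more chart variables and raises the detectable difference.

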## 9.3 Outcomes

Primary	Secondary

• Access to care

• Time of AAD initiation

• Time of OAC initiation

• Time to CA

• Any changes or discontinuation of AAD post-ablation

• Any changes or discontinuation of OAC post-ablation

• Arrhythmia recurrence

• Redo Ablation

	

• Systemic thromboembolic events

• All AF and cardiovascular related hospitalization

• Heart failure exacerbations

• Bleeding complications

• Cardiovascular mortality

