## **4 SELECTION AND ENROLLMENT OF PARTICIPANTS**

### **4.1 Study Enrollment Procedures**

#### **4.1.1 Screening**

Patients will be identified for screening via diagnosis codes for AF on chart review. This can be easily identified by querying current electronic medical record systems. If needed, patients with ICMs can be identified by lists maintained at each study center of those who undergo ICM insertion.

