#### **4.1.2 Consent and Enrollment**

Patients who meet inclusion and exclusion criteria after screening will be directly enrolled in the study. No randomization will occur, but patients will be separated into an ICM and non-ICM arm. We will enroll approximately 2500 patients [n=1250 (ICM) and n=1250 (non-ICM)] from 2018-2021. No consent will be required due to the nature of the study.

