## 5.2 Handling of Study Interventions

Screening, enrollment, and data collection will be performed by the Electrophysiology team and Kansas City Heart Rhythm Research Foundation (KCHRRF) members or respective institutions. Once data is collected, it will be analyzed by KCHRRF staff.

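### Access to care is a primary outcome with no definition, and its only apparent data item is an undated yes/no on EP access, so a difference between arms may reflect selection for an ICM and not an effect of it

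*Combined protocol and SAP*

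**What the plan says.** The outcomes table in 9.3 puts "Access to care" at the head of its primary column, with no definition and no time point. In Table 1 (6.1) the one item about access reads "Access to EP 0 = No, 1 = Yes". It carries no date or window.

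Section 5.1 says what the chart review follows "for 12 months after enrollment": the initial monitoring method, changes in AAD, OAC and CA, recurrence, redo ablation and AF-related complications. Access is not on that list. It is also absent from the primary objective in 1.1 and from the primary outcome named in section 3.

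On how the arms arise, 4.1.2 states "No randomization will occur, but patients will be separated into an ICM and non-ICM arm", and 4.2 adds "ICM is inserted at the discretion of the treating physician". Section 4.1.1 describes screening in general terms: "Patients will be identified for screening via diagnosis codes for AF on chart review". Only if needed does it turn to "lists maintained at each study center of those who undergo ICM insertion". Section 5.2 says "Screening, enrollment, and data collection will be performed by the Electrophysiology team", together with research foundation members or the respective institutions, and does not separate the arms.

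Section 9.4 compares categorical variables by Chi-square at p < 0.05. It mentions Cox models but names no covariates, and no matching is described.

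**The concern.** A primary outcome should be something the ICM could change, measured after the ICM could have changed it. Nothing in the plan places access after entry. A patient who received an ICM had, at the least, reached a physician who chose to implant one. A patient found through an AF code need not have done so. An unadjusted comparison of access can then show a difference even if the ICM has no effect on access.

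Section 2.2 hypothesises that ICM monitoring is superior and should be used for all patients with AF. A significant primary result on access would be read as support for that, and the data could not bear the reading.

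**Working it through.** **The plan's own figure.** Section 9.2 gives 99% power for 2500 patients. It states no event rate or effect size and is not tied to access, so it cannot be reproduced and has no bearing here. Only the 1250 per arm is used below.

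**Step 1: can the item be read as an effect of ICM?** The plan leaves the timing open, so each reading has to be tried.

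- *Read at baseline.* Access then precedes the ICM and cannot be its result.
- *Read during follow-up.* If the implant runs through EP (an assumption, since the plan does not say who inserts the device), the implant contact itself can score Yes. Section 9.1 also lets patients cross into the ICM group at any time, which blurs whether access or ICM came first.
- *Both arms drawn from EP services.* Section 5.2 makes this possible. Access is then near 100% in both arms and there is little or nothing to compare.

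None of the three gives a comparison that can be read as an effect of ICM.

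**Step 2: how small an imbalance would be declared significant?** The plan gives no access proportions, so all those below are assumptions. The test is Pearson Chi-square without continuity correction, which equals z squared, with

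z = (p1 − p2) / √[2 · p̄(1 − p̄) / 1250], where p̄ is the pooled proportion.

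Worked example, 100% v 98%: p̄ = (1250 + 1225)/2500 = 0.99. The standard error is √(2 × 0.99 × 0.01/1250) = 0.00398, so z = 0.02/0.00398 = 5.03.

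Counts are rounded to whole patients.

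| ICM | Non-ICM | Yes counts | Chi-square | z | p |
|---|---|---|---|---|---|
| 100% | 99% | 1250 v 1238 | 12.06 | 3.47 | 0.0005 |
| 100% | 98% | 1250 v 1225 | 25.25 | 5.03 | 5e-7 |
| 100% | 95% | 1250 v 1188 | 63.58 | 7.97 | 1.5e-15 |
| 98% | 97% | 1225 v 1212 | 2.75 | 1.66 | 0.10 |
| 98% | 95% | 1225 v 1188 | 16.30 | 4.04 | 5e-5 |
| 100% | 100% | 1250 v 1250 | no contrast | – | – |

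If every ICM patient has EP access, a shortfall of one point in the other arm is enough. If ICM access is 98%, one point is not enough but three points are. The result turns on proportions that the plan does not give.

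**The case against.** The strongest reply is that this is only a missing definition. No section says that the EP item records the access outcome. Table 1 says openly that its list is not complete, and it also lacks items for other outcomes in 9.3, such as cardiovascular mortality and the times of AAD and OAC initiation. The EP item sits between left atrial size and ejection fraction on one side and OAC compliance, attempted AAD and need for ablation on the other, so it might be meant for follow-up. Access is one of eight items and appears in neither 1.1 nor section 3. What remains could be called the ordinary selection problem of any non-randomised comparison.

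Much of this stands. The link between outcome and item is an inference, though it is the only candidate listed. The timing is unknown.

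A reader might go further and infer that access comes before the ICM and before entry, that the comparison is fixed by how the arms are formed, and that a difference favouring ICM is guaranteed. The documents do not support that. EP access is neither an entry criterion nor an arm definition. AF codes are the general route of screening and insertion lists only a fallback, so the arms are not shown to come from two separate sources. The same EP team may screen both arms.

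The reply fails on one point. Supplying a definition alone would not rescue the item as a primary outcome, because each plausible definition meets one of the difficulties in Step 1.

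**Conclusion.** The concern holds in a limited form. As written, the plan would report a primary result on access that cannot be read as an effect of ICM. The result is liable to be driven by selection or by the implant contact, or it may carry no contrast. Reverse causation is not shown, because the order of access and ICM is not known.

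On size, imbalances of one to three points can reach p < 0.05 with 1250 per arm, depending on the level in the ICM arm. The 98% v 97% case shows that significance is not assured.

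This rests on two assumptions: that the EP item is the intended measure of access, and that selection could shift access by a few points. The point bears on one of eight primary outcomes.

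**What to change.** 1. In 9.3, remove access to care from the primary outcomes.
2. In 6.1, record EP access as of the index date as a baseline variable, and state what that date is in each arm.
3. In 9.4, report it by arm and name it as an adjustment covariate in the outcome models. If nearly everyone in both arms has access, the adjustment will change little, and the table by arm will show that.
4. If access is kept as an outcome, make it secondary and descriptive, with a stated window after the index date. State that it will not be read as evidence of ICM benefit.

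The cost is one of eight primary outcomes, some wording in 6.1, 9.3 and 9.4, and one dated baseline item from the chart.

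Two larger changes are not needed. Making prior EP contact an entry condition would alter the study population, although 2.2 concerns all patients with AF. Counting EP visits after the index date would require abstraction visit by visit.
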